10.4.2 Analysis of Secondary Endpoints

The following secondary endpoints will be analyzed for this study:

- Retear rate at 3, 12 and 24 months post-operative will be summarized and presented as per the Primary Endpoint analysis.
- OSS, WORC/C-WORC, Constant, SSV and EQ-5D-5L PRO scores will be calculated and summarized for each visit using descriptive statistics for continuous variables, separately for the ARCR augmented with REGENETEN group and the ARCR alone (standard of care) group. Changes from baseline to each subsequent follow up visit will be similarly summarized. Repeated measures ANCOVA models will be used to assess statistical significance in the change from baseline to each time point. The null hypothesis will be that there is no difference between baseline and the respective time point. An estimate of the LS mean difference between the time points for the scores will be reported, along with the corresponding 95% confidence interval and p-value. A separate model will be used to assess statistical significance between the treatment groups at each time point. Minimal Clinically Important Differences will be assessed and presented where appropriate.
- Patient satisfaction and return to work questionnaire will be presented as number and percentage of patients who have selected each of the responses at each time point. The duration a patient has taken away from work will be summarized descriptively.
- VAS Pain score (1-100mm) will be summarized at baseline, 2 and 6 weeks, 3, 6, 12 and 24 months using descriptive statistics for continuous variables. Change from baseline to each follow up assessment will be similarly summarized and p-values will be presented.

CONFIDENTIAL AND PROPRIETARY

Study Protocol	Smith-Nephew
A Prospective, Multi-center, Randomized Controlled	Number:
Study to Evaluate the Safety and Efficacy of ARCR	REGENETEN.2020.01
augmented with REGENETEN™ Bioinductive Implant	Version: 2.0, 08 Dec
System in Full-thickness Tears (large or massive) Repair	2021
	Page: 73 of 134

- MRI analysis will be conducted by an external vendor at baseline, 3, 6, 12 and 24 months and will be presented appropriately for continuous or categorical variables.
- Opioid use will be collected each day for 2 weeks following surgery. The number of days
 of opioid use will be calculated for each patient and this will be presented descriptively for
 all patients, by treatment type (ARCR augmented with REGENETEN or ARCR alone).
- Total operative time will be calculated for each treatment arm and presented descriptively.
- The type of sling will be collected and presented for each treatment arm summarizing if standard sling, shoulder immobilizer, abduction sling, ER sling, or other were advised and mobilization time will be calculated for both arms summarizing mobilization duration.

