8.3.2 Secondary Endpoints

The secondary study endpoints are:

- The cumulative 3, 12, and 24 months retear rate after full-thickness ARCR augmented with REGENETEN (confirmed on MRI) versus ARCR alone;
- Overall performance of full-thickness ARCR augmented with REGENETEN versus ARCR alone at Baseline and at 3, 6, 12 and 24 months assessed by:
 - Oxford Shoulder Score (OSS),
 - Western Ontario Rotator Cuff (WORC)/Chinese version WORC (C-WORC) Index,
 - Constant-Murley Score,
 - Subjective shoulder value (SSV),
 - o EuroQol 5 Dimension 5 Level (EQ-5D-5L) Score,
 - Patient satisfaction Questionnaire,
 - Pain, Visual analog scale (VAS) Score (additionally at baseline, 2 weeks, 6 weeks, 3 months and 6 months);
- MRI Tendon Findings in ARCR augmented with REGENETEN versus ARCR alone postoperatively at Baseline, 3, 6, 12 and 24 months including:
 - Sugaya score,

CONFIDENTIAL AND PROPRIETARY

Study Protocol	Smith-Nephew
A Prospective, Multi-center, Randomized Controlled	Number:
Study to Evaluate the Safety and Efficacy of ARCR	REGENETEN.2020.01
augmented with REGENETEN™ Bioinductive Implant	Version: 2, 08 Dec 2021
System in Full-thickness Tears (large or massive) Repair versus ARCR alone	Page: 49 of 134

- Goutallier grading,
- o Total tendon thickness, tendon length,
- Size of retear (anteroposterior [AP]/mediolateral [ML]),
- Shape of retear;
- Outcome of Return to Work Questionnaire in ARCR augmented with REGENETEN versus ARCR alone (additionally at 2 and 6 weeks);
- Cumulative duration of opioid use in ARCR augmented with REGENETEN versus ARCR alone at 2 weeks postoperatively;
- Total operative time in ARCR augmented with REGENETEN versus ARCR alone;
- Sling type and mobilization time in ARCR augmented with REGENETEN versus ARCR alone.

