10.4 EFFICACY ANALYSIS

10.4.1 Analysis of Primary Endpoint

A binary variable will be defined based on whether each patient has a Sugaya score of Type IV or V retear/recurrence. This variable will be used to present the number of retears at the 6 month post-operative visit, together with a percentage and 95% confidence interval for a single proportion (calculated using the Clopper-Pearson Exact method).

To test whether ARCR augmented with REGENETEN is superior to ARCR alone, the null hypothesis is that the retear rate of the ARCR augmented with REGENETEN group is not better than, or the same as, the retear rate of the ARCR alone group (standard of care)::

$$H_0: \mu - \mu_0 \ge 0$$

$$H_1$$
: $\mu - \mu_0 < 0$

In the stated hypothesis, μ represents the rate of retear for those patients which received REGENETEN and μ_0 represents the rate of retear for the standard of care group. A binary variable of success/failure will be created to fit a logistic model adjusting for differences in baseline characteristics.

CONFIDENTIAL AND PROPRIETARY

Study Protocol	Smith-Nephew
A Prospective, Multi-center, Randomized Controlled	Number:
Study to Evaluate the Safety and Efficacy of ARCR	REGENETEN.2020.01
augmented with REGENETEN™ Bioinductive Implant	Version: 2.0, 08 Dec
System in Full-thickness Tears (large or massive) Repair	2021
versus ARCR alone	Page: 72 of 134

As a further analysis of the primary endpoint, the time taken for retear to occur will be assessed as a survival endpoint for both treatment groups in order to compare the trend of incidence of retear over time.

Analysis will be carried out using the FAS and PP population.

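### VAS pain is a device-versus-control endpoint, yet its only stated p-values follow change from baseline; for five further scores the between-arm estimate and its baseline adjustment are left unspecified

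*Combined protocol and SAP*

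**What the plan says.** Section 8.3.2 frames the endpoint as "Overall performance of full-thickness ARCR augmented with REGENETEN versus ARCR alone at Baseline and at 3, 6, 12 and 24 months assessed by" a list that holds OSS, WORC/C-WORC, Constant-Murley, SSV, EQ-5D-5L, patient satisfaction and VAS pain. VAS pain and the five scores are therefore comparisons of the two arms by definition.

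Section 10.4.2 gives the analyses:

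- **Five scores.** A repeated measures ANCOVA addresses change from baseline, with its null spelled out: "The null hypothesis will be that there is no difference between baseline and the respective time point". The LS-mean difference to be reported with a 95% CI and p-value is the one between time points. The arms are then covered in one sentence: "A separate model will be used to assess statistical significance between the treatment groups at each time point". No model form, covariate or effect estimate is attached to it.
- **VAS pain.** "Change from baseline to each follow up assessment will be similarly summarized and p-values will be presented". The bullet names no arm comparison and, unlike the scores bullet, does not say that summaries are given by arm.
- **Retear at 3, 12 and 24 months.** "Retear rate at 3, 12 and 24 months post-operative will be summarized and presented as per the Primary Endpoint analysis". Section 10.4.1 sets that analysis up between arms: "To test whether ARCR augmented with REGENETEN is superior to ARCR alone".
- **Others.** These are descriptive. Satisfaction and return to work "will be presented as number and percentage of patients who have selected each of the responses at each time point"; for surgery duration, "Total operative time will be calculated for each treatment arm and presented descriptively".

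Section 10 presents itself as a short account, with detail left to an SAP that must be final before database lock.

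**The concern.** Both arms have a rotator cuff repair, so pain and function should change after surgery whether or not the implant helps. A test of baseline against follow-up measures that shared change. If it supplies the only p-values for VAS pain, the report can show significant results at every visit and still say nothing about augmentation against repair alone.

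For the five scores the gap is smaller. The arms are to be compared, but the estimate and interval that the text specifies belong to the change from baseline. A reader of the results would get a size of effect for surgery and perhaps only a p-value for the device. If the arm comparison also ignores the baseline score, it loses precision for no reason, because section 9.1.2 collects all six measures before surgery.

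Section 2 says the results are to support registration in China and reimbursement, and both uses turn on the contrast between arms. Section 10.4.3 also applies the secondary-endpoint analysis to the at-risk groups, so the gap carries over to them.

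**Working it through.** **Inputs.** 130 subjects per arm (section 11) and a two-sided 5% level (section 10.1). The plan gives no mean change, SD or correlation for VAS pain or the scores, so it has no figure of its own to reproduce. The standardized changes and correlations below are assumptions, shown as ranges.

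**1. What a change-from-baseline test shows when the implant does nothing.** Let d be the mean change divided by the SD of the change, equal in both arms. In one arm, z = d × √130. For d = 0.5, z = 0.5 × 11.40 = 5.70, a two-sided p of about 1e-8. The text does not say whether the model is fitted by arm or to both arms together. Pooled, z = 0.5 × √260 = 8.06. Neither version compares the arms.

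The chance of significance in a given arm is w = Φ(d√130 − 1.96) + Φ(−d√130 − 1.96). The arms are independent, so both are significant with probability w², and exactly one with probability 2w(1 − w).

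| Assumed d | Given arm, w | Both arms | Exactly one arm | Between-arm test |
|---|---|---|---|---|
| 0.25 | 0.81 | 0.66 | 0.30 | 0.05 |
| 0.30 | 0.93 | 0.86 | 0.13 | 0.05 |
| 0.50 | 0.9999 | 0.9998 | 0.0002 | 0.05 |
| 0.80 | about 1.00 | about 1.00 | about 0 | 0.05 |

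The fourth column for d = 0.25 is 2 × 0.8134 × 0.1866 = 0.30. With a modest change, then, there is a 30% chance that one arm is significant and the other is not although the device has no effect. That pattern is easily misread as a difference between arms.

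**2. What baseline adjustment is worth.** Let ρ be the correlation of baseline with follow-up.

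- Against an unadjusted comparison of follow-up scores, residual variance falls from σ² to σ²(1 − ρ²), a cut of ρ². For ρ = 0.3 this is 0.09, or 9%. For ρ = 0.6 it is 0.36, or 36%.
- Against an unadjusted comparison of change scores with equal SDs, variance falls from 2σ²(1 − ρ) to σ²(1 − ρ²), a cut of (1 − ρ)/2. This is 35% at ρ = 0.3 and 20% at ρ = 0.6.
- With 130 per arm, the between-arm difference detectable with 80% power is (1.96 + 0.84) × √(2/130) = 0.35 SD unadjusted. Multiplying by √(1 − ρ²) gives 0.33 SD at ρ = 0.3 and 0.28 SD at ρ = 0.6.

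**3. Endpoint against stated test.**

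| Endpoint (section 8.3.2, versus control) | Test in section 10.4.2 | Between-arm estimate with CI specified |
|---|---|---|
| VAS pain | p-values after change from baseline | No |
| Five scores | Change from baseline, plus a between-group model | No; the LS-mean difference is between time points |
| Retear at 3, 12, 24 months | As primary, between arms | Not at issue |
| Satisfaction, return to work, MRI findings, opioid days, operative time, sling | Descriptive | Not at issue |

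**The case against.** The strongest reply is that the plan does compare the arms. The bullet that holds the baseline null goes on to name a between-group model for all five scores, and secondary retear follows the primary between-arm analysis. This stands. A reader might infer from the quoted null that the secondary endpoints in general are tested only within arm, so that any significance reflects surgery. The documents do not support that.

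A reader might also infer that the arms will be compared by a different model at each visit, losing the correlation between visits and dropping subjects who miss one. That is not supported either. The text speaks of one separate model, which can mean separate from the change-from-baseline model, and a single longitudinal model with contrasts at each visit fits it.

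Nor do endpoints planned as descriptive need a test. Opioid days and operative time have no baseline and no planned p-value, and describing them by arm is a defensible choice.

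For VAS pain, the p-values could be meant to compare the arms' changes. The sentence does not exclude this, but nothing in the bullet mentions a treatment contrast. The natural reading is change from baseline, and either way the contrast must be named.

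Finally, section 10 is a summary with the SAP to follow, so an unstated baseline term is not proof of an unadjusted analysis. That is fair for the model detail. It does not repair the VAS sentence, which states an analysis that does not match its endpoint. The study is unblinded (section 8.2.2), and the SAP need only be final before database lock, so early specification is also the safer course.

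**Conclusion.** The point holds for six measures. Followed as written, the VAS pain analysis does not answer the comparison that section 8.3.2 sets. For OSS, WORC/C-WORC, Constant, SSV and EQ-5D-5L the comparison is planned, but its estimate, interval and baseline adjustment are not specified, while the change from baseline has a written null and an LS-mean difference with CI.

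The size rests on assumptions. With no device effect and 130 per arm, a change-from-baseline test is significant in a given arm with probability 0.81 at a change of 0.25 SD and 0.9999 at 0.5 SD, against 0.05 for a between-arm test. The 9% to 36% variance saving assumes a correlation of 0.3 to 0.6 and an unadjusted follow-up comparison as the alternative, which the plan neither states nor rules out.

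The primary endpoint, the secondary retear rates and the descriptive endpoints are not affected.

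**What to change.** In section 10.4.2 and the SAP, for VAS pain and the five scores:

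- Fit one repeated-measures model per measure with arm, visit, arm-by-visit and the baseline score.
- Make the between-arm LS-mean difference with 95% CI at each visit the reported secondary result, with the null stated as no difference between arms.
- Label change-from-baseline tests in the randomized arms descriptive. They keep a natural place in the single-arm revision group, which has no comparator.

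For VAS pain, also settle which visits apply. Sections 8.3.2 and 10.4.2 include 12 and 24 months, but the procedure lists in sections 9.1.8 and 9.1.9 do not name the VAS pain score.

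The cost is SAP wording and programming. The baseline values are already collected, and the model change needs no additional subjects or measurements.

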9.2.6 Patient Satisfaction Questionnaire

The Patient Satisfaction Questionnaire is a simple subjective assessment of the success of surgery from the patient's perspective. It has not been formally validated [42].

Pre-Op:

CONFIDENTIAL AND PROPRIETARY

Study Protocol	Smith-Nephew
A Prospective, Multi-center, Randomized Controlled	Number:
Study to Evaluate the Safety and Efficacy of ARCR	REGENETEN.2020.01
augmented with REGENETEN™ Bioinductive Implant	Version: 2.0, 08 Dec
System in Full-thickness Tears (large or massive) Repair	2021
versus ARCR alone	Page: 65 of 134

The Patient satisfaction pre-Op will be documented on a visual analogue score of 0-100 'How satisfied are you with your medical care?' Rated by the subject with 0 is the least satisfied, 100 the most satisfied [43].

Post-Op:

This includes the VAS Patient Satisfaction Score as for pre-Op and additional five questions ask of the patient:

- 1. How well did the surgery relieve the pain?
- 2. How well did the surgery increase your ability to perform regular activities?
- 3. How well did the surgery allow you to perform heavy work or sport activities (if allowed by Dr)?
- 4. How well did the surgery meet your expectations?

Questions rated by the patient with excellent, very good, good, fair and poor.

5. Would you have the operation again if needed on another joint?

Question rated by the patient with Definitely yes, Probably yes, Possibly not, Definitely not [42].

A paper questionnaire will be provided by the Sponsor to be completed by the subject. Responses will be recorded in the eCRF.

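### Section 10.4.2 gives the whole satisfaction questionnaire a response-percentage rule that does not fit its 0-100 VAS, and states no change from baseline or between-arm estimate for that item

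*Combined protocol and SAP*

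**What the plan says.** Section 9.2.6 describes a mixed-format instrument. Before surgery: "The Patient satisfaction pre-Op will be documented on a visual analogue score of 0-100". After surgery: "This includes the VAS Patient Satisfaction Score as for pre-Op and additional five questions ask of the patient". For the first four of those five questions the scale is "Questions rated by the patient with excellent, very good, good, fair and poor"; the fifth has four ordered options. Sections 9.1.2 and 9.1.6 to 9.1.9 administer the questionnaire at baseline and at 3, 6, 12 and 24 months.

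Section 8.3.2 places satisfaction among the secondary endpoints under the lead-in "Overall performance of full-thickness ARCR augmented with REGENETEN versus ARCR alone at Baseline and at 3, 6, 12 and 24 months assessed by", so it is listed as a device-versus-control comparison.

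Section 10.4.2 then states, for every visit: "Patient satisfaction and return to work questionnaire will be presented as number and percentage of patients who have selected each of the responses". That bullet also adds a separate descriptive summary for time away from work, but nothing for the satisfaction VAS. The bullet for the other scores reads "OSS, WORC/C-WORC, Constant, SSV and EQ-5D-5L PRO scores will be calculated and summarized for each visit using descriptive statistics for continuous variables". It goes on to change from baseline, repeated-measures ANCOVA, and "A separate model will be used to assess statistical significance between the treatment groups at each time point". Satisfaction is not in that list.

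**The concern.** A rule that counts how many patients chose each response assumes a short list of responses. A VAS from 0 to 100 has none. Taken at its word, the plan would print a long frequency table for the VAS in each arm at each visit, from which an arm comparison cannot sensibly be read.

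The VAS is also the only part of the questionnaire with a baseline value, and so the only part for which a change or a baseline-adjusted comparison is possible. If the sentence is carried unchanged into programming, a secondary endpoint listed as comparative, and collected at five visits, would have no stated estimate of the arm difference and no confidence interval for that item. The analyst would have to choose one later, in an unblinded trial (section 8.2.2), when the choice should have been made in advance.

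**Working it through.** The plan gives no figure for the satisfaction analysis, so there is nothing to reproduce. The check compares the stated rules and then sizes the literal table.

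**Rules for 0-100 items, side by side**

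| Item | Scale | Stated analysis in 10.4.2 |
|---|---|---|
| SSV (9.2.5) | single item, 0-100% | continuous summaries, change from baseline, ANCOVA, between-arm model |
| Pain VAS (9.2.7) | 0-100 | continuous summaries, change from baseline with p-values |
| Satisfaction VAS (9.2.6) | 0-100 | number and percentage per response |
| Five post-operative satisfaction questions (9.2.6) | 5 or 4 categories | number and percentage per response |

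The rule fits the last row and not the one above it. At baseline the VAS is the only satisfaction item, so the rule has nothing else to act on there.

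**How thin the literal table would be**

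Inputs: 130 subjects per arm (section 11); a VAS from 0 to 100 (section 9.2.6). Recording in whole points is an assumption and gives 101 possible values.

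- VAS: 130 / 101 = 1.29 subjects per possible value per arm.
- Questions with five categories: 130 / 5 = 26 per category on average.
- Question with four categories: 130 / 4 = 32.5 per category on average.
- Revision group: section 10.4.3 presents it in the same way as the secondary endpoints, with at most 40 subjects, so at most 40 / 101 = 0.40 per possible value.

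Scores cluster, so the average over all 101 values is only a guide. The documents give no mean or SD for this scale. Four assumed normal distributions, rounded and clipped to 0-100, were simulated (4,000 arms of 130 each):

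| Assumed mean / SD | Distinct values occupied | Share of occupied values with fewer than 5 subjects |
|---|---|---|
| 50 / 30 | 68 | 96% |
| 70 / 20 | 57 | 92% |
| 85 / 15 | 41 | 84% |
| 90 / 10 | 31 | 65% |

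The table stays sparse in every case.

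**What a continuous analysis would give**

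For an unadjusted mean difference with all 130 per arm observed, SE = SD × √(2/130). The 95% CI half-width is 1.96 × SE. The difference detectable with 80% power at two-sided 5% is (1.96 + 0.84) × SE. With an assumed SD of 20: SE = 20 × 0.124 = 2.48, half-width 4.9 points, detectable difference 6.9 points.

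| Assumed SD | CI half-width (points) | Detectable difference (points) |
|---|---|---|
| 15 | 3.6 | 5.2 |
| 20 | 4.9 | 6.9 |
| 25 | 6.1 | 8.7 |
| 30 | 7.3 | 10.4 |

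The data already planned would therefore support an interpretable arm contrast.

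**The case against.** The best defence is that section 10.1 already covers the VAS. It sets a default of n, mean, median, SD, minimum and maximum for continuous variables, with point estimates and 95% confidence intervals where appropriate. A mark on a line is not naturally a response that a patient selects, so section 10.4.2 can be read as speaking only to the questions with listed options. This partly stands. A reader might infer that the plan rules out a mean for the VAS; the documents do not support that. But section 10.4.2 states its rule for the whole questionnaire and makes its one descriptive exception for time off work, not for the VAS, so the two sections remain unreconciled. The default also names no change from baseline and no arm contrast.

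Second, section 10 calls itself a brief description and defers detail to a SAP to be finalized before database lock. That is fair, and it makes this an easy correction. It would be wrong to infer that no arm comparison of satisfaction will ever be made. The difficulty is that the present sentence is a stated rule of the wrong type, not a silence, and a SAP that follows it would inherit the mismatch.

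Third, a reader might take the VAS to be the questionnaire's main item. Nothing in section 9.2.6 ranks it so. It asks about satisfaction with medical care, while the five added questions ask directly about the result of surgery. A change from a score given before the operation is thus open to debate as a measure of surgical success. That point stands for the change score. It weighs less against a baseline-adjusted arm difference: in a randomised comparison, the baseline serves as a covariate and need not mean the same thing before and after surgery.

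Fourth, other secondary endpoints, such as opioid days and operative time, are also only described, and the pain VAS bullet names no between-arm model. So the absence of an arm contrast is not peculiar to satisfaction. What is peculiar is a summary rule that does not match the type of variable.

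**Conclusion.** The point holds as a mismatch between sections 9.2.6 and 10.4.2 that concerns the VAS item. The rule is sound for the five categorical questions. For the VAS, its literal application gives 1.3 subjects per possible value per arm, with about 31 to 68 occupied values under the assumed distributions. On the more generous reading through section 10.1, the VAS gets a mean and SD, but still no stated change from baseline or between-arm estimate.

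The sparsity figures rest on whole-point recording and, for the simulated range, on assumed means and SDs. They describe how readable a table would be, not an effect on a trial conclusion. The impact is minor: one item among many secondary endpoints, from a questionnaire that section 9.2.6 itself says has not been formally validated. The primary endpoint, sample size and data collection are unaffected.

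**What to change.** Split the sentence in section 10.4.2 and carry the same wording into the SAP:

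- For the five post-operative categorical questions, keep number and percentage per response, by arm and visit.
- Add the satisfaction VAS (0-100) to the bullet for OSS, WORC/C-WORC, Constant, SSV and EQ-5D-5L: continuous summaries by arm, change from baseline, and a between-arm mean difference with 95% CI at 3, 6, 12 and 24 months, adjusted for the baseline VAS.

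The cost is a wording change and one more run of a model already planned. No new data are needed. It should be settled before database lock, when the SAP is due to be final.

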9.1.9 Postoperative Follow-Up Visit 8 (24 Months [730 ± 60 days])

- 1. Query subject regarding any changes in general health and the use of concomitant medications. If any AEs, ADEs or DDs are observed or reported, they must be recorded as instructed in Section 12 Adverse Events and Device Deficiencies.
- 2. Complete the Constant-Murley Questionnaire (Physician/Examiner completed portion).
- 3. Have the subject complete the OSS Questionnaire.
- 4. Have the subject complete the WOR/C-WORC Questionnaire.
- 5. Have the subject complete the subjective part of Constant-Murley Questionnaire.
- 6. Have the subject complete the SSV Questionnaire.

CONFIDENTIAL AND PROPRIETARY

Study Protocol	Smith-Nephew
A Prospective, Multi-center, Randomized Controlled	Number:
Study to Evaluate the Safety and Efficacy of ARCR	REGENETEN.2020.01
augmented with REGENETEN™ Bioinductive Implant	Version: 2.0, 08 Dec
System in Full-thickness Tears (large or massive) Repair	2021
versus ARCR alone	Page: 60 of 134

- 7. Have the subject complete the EQ-5D-5L Questionnaire.
- 8. Have the subject complete Patient satisfaction Questionnaire.
- 9. Have the subject complete the Return to Work Questionnaire (if appropriate).
- Complete MRI assessment.
- 11. If any Reoperation occurred complete reoperation CRF.
- 12. Complete Exit Visit CRF and inform subject of End of Study.

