9.2.10 Return to Work Questionnaire

Generic questionnaire, covering work related questions, including demographics on laborer/sedentary [42].

- Were you working before surgery? Y/N
 - a. If yes, what was your job type and the nature of your work?
- 2. Have you returned to work? Y/N

CONFIDENTIAL AND PROPRIETARY

Study Protocol	Smith-Nephew
A Prospective, Multi-center, Randomized Controlled	Number:
Study to Evaluate the Safety and Efficacy of ARCR	REGENETEN.2020.01
augmented with REGENETEN™ Bioinductive Implant	Version: 2.0, 08 Dec
System in Full-thickness Tears (large or massive) Repair	2021
versus ARCR alone	Page: 67 of 134

- a. If yes, how long after your operation did you return to work
- b. if you couldn't get back to work was there a particular reason?
- 3. Have you been able to return to the job you did before your surgery (doing the same activities)? Y/N
 - a. If No, is there a particular reason you couldn't return to the same activities?
- 4. If RTW, did you feel ready to go back to work physically? Y/N
- 5. Since returning to work, did you have to take further time off due to shoulder pain or weakness? Y/N
 - a. If so, how long?

A paper questionnaire will be provided by the Sponsor to be completed by the subject. Responses will be recorded in the eCRF.

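### The planned summary of time off work can only cover subjects who went back, so its between-arm contrast can hide a difference, or reverse it if one arm's extra returners come back late

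*Combined protocol and SAP*

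**What the plan says.** Section 8.3.2 lists the endpoint as a comparison: "Outcome of Return to Work Questionnaire in ARCR augmented with REGENETEN versus ARCR alone".

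Section 10.4.2 plans two summaries in one bullet. The questionnaire answers are to be "presented as number and percentage of patients who have selected each of the responses at each time point". For time off work: "The duration a patient has taken away from work will be summarized descriptively". It states no population, denominator or rule for subjects still off work, and no test or estimate of a difference in duration.

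Section 9.2.10 shows what can be summarised:
- Item 1 asks whether the subject was working before surgery.
- Item 2 asks whether the subject has returned. Item 2a follows a yes: "If yes, how long after your operation did you return to work". Item 2b is for those who have not returned: "if you couldn't get back to work was there a particular reason".
- Item 5 concerns later absence: "Since returning to work, did you have to take further time off due to shoulder pain or weakness".

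Elsewhere the plan does use a time-to-event method. In Section 10.4.1, "the time taken for retear to occur will be assessed as a survival endpoint for both treatment groups". Return to work gets no such treatment.

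**The concern.** Time to return is a censored quantity. A subject still off work at 24 months, or when last seen, has been absent at least that long, but the form records only a reason. A mean or median of the recorded durations therefore leaves out the longest absences. It also selects subjects on something that happens after randomisation, so the two groups being averaged are no longer the randomised groups.

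If the arms differ in the share who return, the duration figures can look alike when time off work differs. They can also point the opposite way: an arm that gets slow recoverers back to work adds long durations to its own average, while the other arm's non-returners add nothing. Readers will set the two figures side by side, because the endpoint is worded as a comparison.

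**Working it through.** The documents give no figure for time off work, so there is none to reproduce. They also give no return proportions, no return times and no share working before surgery. All such inputs below are assumptions. Only the 24-month follow-up comes from the protocol. Every subject in the examples is followed to the horizon.

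**Masking.** Assume a fraction p returns after a mean of 4 months and the rest are still off at 24 months. The returners-only mean is 4 months whatever p is. The mean over 24 months, counting everyone, is p × 4 + (1 − p) × 24:
- p = 0.90: 3.6 + 2.4 = 6.0 months
- p = 0.80: 3.2 + 4.8 = 8.0 months
- p = 0.75: 3.0 + 6.0 = 9.0 months

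So 90% versus 75% returning gives 4 versus 4 months on the planned summary, against 6.0 versus 9.0 months. At 90% versus 80% it is again 4 versus 4, against 6.0 versus 8.0.

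**Reversal.** Take 100 workers per arm and a horizon of 104 weeks.
- ARCR alone: 25 return at 8 weeks, 25 at 16, 20 at 26; 30 do not return.
- REGENETEN: the same 70, plus 20 who return at 40 weeks; 10 do not return.

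Time off among the shared 70 totals 25 × 8 + 25 × 16 + 20 × 26 = 1,120 weeks.

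| | ARCR alone | REGENETEN | Difference |
|---|---|---|---|
| Mean, returners only | 1,120 / 70 = 16.0 | (1,120 + 800) / 90 = 21.3 | +5.3 weeks |
| Restricted mean, all workers | (1,120 + 30 × 104) / 100 = 42.4 | (1,920 + 10 × 104) / 100 = 29.6 | −12.8 weeks |
| Median, returners only | 16 | 16 | 0 |

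The returners-only mean makes REGENETEN look 5.3 weeks worse when it is 12.8 weeks better. The median shows no difference.

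**When the sign flips.** Let e be the extra fraction returning on REGENETEN, L their return time in weeks, 16 weeks the mean of the other returners, and q the REGENETEN non-return fraction. Then:
- returners-only difference = e × (L − 16) / (1 − q)
- restricted-mean difference = e × (L − 104)

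With e = 0.20, L = 40 and q = 0.10 these give 0.20 × 24 / 0.90 = +5.3 and 0.20 × (−64) = −12.8, as in the table. The second is negative for any return before 104 weeks. The first is positive only if L exceeds 16. Late extra returners therefore reverse the sign; extra returners at the average time give a tie.

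The range examined was non-return of 10% to 30% on ARCR alone, 5% to 20% on REGENETEN (always the lower of the two), and L of 26, 40 or 52 weeks. The returners-only difference ran from +0.5 to +9.5 weeks and the restricted-mean difference from −2.6 to −19.5 weeks. The sign reversed in every case because every L was set above 16.

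**The case against.** **Section 10.4.2 does not say the summary is limited to returners.** This stands as a matter of wording. The limit follows from items 2a and 2b, and Section 10 calls itself a brief description with detail left to a SAP. But the form supplies no other duration, and nothing in the text says how one would be assigned to a subject still off work.

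**Non-returners do not vanish from the report.** Correct. The same bullet tabulates the return answer at each visit, so 90% versus 75% would be visible. That table does not correct the duration figure, and neither summary is stated to be confined to subjects working before surgery.

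**No comparison of duration is tested.** Also correct. A reader might infer that a formal result could come out wrong. The documents do not support that: no p-value and no part of the primary conclusion depends on this summary. The risk is a misleading descriptive contrast.

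**Reversal is built into the assumptions.** This stands. It needs late extra returners, and the median in the example did not reverse. Section 10.1 lists both mean and median as standard summaries. Masking needs only unequal return proportions, with similar return times among those who go back.

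**Absenteeism costs.** A reader might infer that this duration feeds the health-economic results. Section 21.4.2 lists absence from work costed at the mean wage, but does not name this summary as the source. The health-economic endpoints in Section 10.4.3 do not name absenteeism. The link is not established.

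**Conclusion.** The concern holds in a limited form. As the data are collected, the planned duration summary can describe only subjects who have returned, and the plan has no rule for those who have not. Unequal return proportions can then hide a real difference in time off work (4 versus 4 months against 6.0 versus 9.0 in the illustration). The sign can reverse if one arm's extra returners come back later than average (+5.3 against −12.8 weeks). These sizes rest wholly on assumed inputs; the mechanism does not.

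This affects one descriptive secondary endpoint. It is worth correcting because a better summary is available from data already planned, and the protocol already uses that type of method for retear.

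**What to change.** Replace the descriptive duration summary in Section 10.4.2, and carry the change into the SAP, as follows:
- **Population:** subjects working before surgery (item 1).
- **Analysis:** time from operation to first return to work, by Kaplan-Meier in each arm, censored at last contact.
- **Estimate:** restricted mean time to first return by arm, with the difference and 95% CI, and the proportion not returned alongside.
- **Horizon:** a fixed time that follow-up supports. The last visit is at 730 ± 60 days (Section 9.1.9), so a subject can finish within the window at 730 − 60 = 670 days and is then not observed to a full 24 months.
- **Reoperation:** state how these subjects are handled, since Section 7.8.1 keeps data after reoperation out of the study data.
- **Further time off (item 5):** report separately. It is not part of time to first return.

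The cost is SAP wording and a little more analysis, with no new data collection. The method assumes that censoring at last contact is non-informative. That may fail if subjects doing badly leave the study, so the assumption should be stated.
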